## 1. INTRODUCTION

The purpose of this reporting and analysis plan (RAP) is to describe the analyses to be included in the Clinical Study Report for Protocol 207597:

Protocol Revision Chronology:		
2017N311825_00	2017-MAR-06	Original
2017N311825_01	2017-JUN-02	To address clarifications regarding the aim of the study, the eligibility criteria, the schedule of activities, the clinical assessments, and the recording of lab data and adverse events. The benefit: risk section was also updated based on the Part 2 results from study CNTO7160ASH1001. Also, a few typographical errors were corrected.
2017N311825_02	2017-SEP-13	To add more information on the risk: benefit section and the study design justification sections. To address clarifications regarding the unblinding of treatment in case of emergency. To clarify that rechallenge is not allowed once the treatment discontinuation criteria are met. Also, a few typographical errors were corrected.

## 2. SUMMARY OF KEY PROTOCOL INFORMATION

### 2.1. Changes to the Protocol Defined Statistical Analysis Plan

Changes from the originally planned statistical analysis specified in the protocol are outlined in [Table 1](#).

**Table 1 Changes to Protocol Defined Analysis Plan**

Protocol	Reporting & Analysis Plan	
Statistical Analysis Plan	Statistical Analysis Plan	Rationale for Changes
Modified Intent to Treat population.	Modified Intent to Treat (Loss of Control), Modified Intent to Treat and Safety excluding GCP non-compliant subjects populations.	The Modified Intent to Treat (Loss of Control) was added to account for the intercurrent event when participants receive the wrong study treatment. Whilst the data from GCP non-compliant participants should not be used in the efficacy analysis, the participants were dosed with GSK3772847 or Placebo so all safety data (AEs, SAEs, ECGs etc.) should be reported.
Section 10.4.1 of the protocol describes a sensitivity analysis where data is analysed as missing and worst case (loss of control) for participants who withdraw from the study for reasons other than loss of asthma control.	A primary and secondary estimand have been defined to capture where data is analysed as missing and worst case (loss of control) for various intercurrent events where participants withdraw from the study for reasons other than loss of asthma control.	The protocol was approved before the ICH E9 addendum on estimands. The RAP is performing the same planned analysis as detailed in the Protocol however the terminology has been updated in accordance with ICH E9.
Statistical analysis would be performed for each screening eosinophil strata separately.	Bayesian analysis will include screening eosinophil strata as a covariate instead of performing split analysis models.  In addition, an exploratory analysis using fractional polynomials was added to examine the relationship between loss of control and screening eosinophils (continuous), IgE and FeNO.	Bayesian analysis will now include the same covariates as the frequentist analysis.  By modelling eosinophils as a continuous endpoint, it will provide more information on the impact of varying screening eosinophil levels on the treatment effect. It will also provide additional information on the role of IgE and FeNO on loss of asthma control.

Protocol	Reporting & Analysis Plan	
Statistical Analysis Plan	Statistical Analysis Plan	Rationale for Changes

Mixed model repeated measures will be used to analyse the following endpoints. The baseline value of each endpoint will be included along with baseline*visit and treatment*visit interactions. Treatment differences, 95% confidence intervals and p-values will be presented.
 
 
• Change from baseline in ACQ-5 absolute score
 
• Change from baseline in SGRQ total score
 
• Change from baseline in Pre-bronchodilator FEV1
 
• Change from baseline in FeNO
 
	
FEV1 and FeNO will only be analysed up until Week 4 (down titration of ICS), all data post Week 4 will be summarised descriptively only.
 
In addition, an exploratory analysis using fractional polynomials was added to examine the relationship between FEV1 at Week 4 with screening eosinophils (continuous), IgE and FeNO.
 
Continuous ACQ-5 and SGRQ will only be summarised and will not be analysed.
	
FEV1 and FeNO are impacted by ICS, so including change from baseline post-down titration of ICS would be confounding change due to study treatment with change due to ICS. To better explore the data prior to down titration, the fractional polynomial analysis has been added to examine the relationship between FEV1 at Week 4 with screening eosinophils (continuous), IgE and FeNO.
 
FEV1, FeNO, ACQ-5 and SGRQ analysed using an MMRM would be assuming that data is missing at random. In fact, participants could have withdrawn due to loss of asthma control which is related to study treatment, so the analysis assumptions would not have been valid.

Secondary endpoints listed as:
 
 
• Serum concentrations of GSK3772847 at weeks 2, 4, 8, 12, 16, 20, 24 and 28.
 
• Free and total soluble ST2 levels at weeks 2, 4, 8, 12, 16, 20, 24 and 28.
 
	
Secondary endpoints listed as:
 
 
• Serum concentrations of GSK3772847 by nominal time.
 
• Free and total soluble ST2 levels in serum by nominal time.
 
	
Endpoint updated to use nominal time so that all data collected is summarised.


Proportion of participants with loss of asthma control assessed over Weeks 0-16 only.
	
Proportion of participants with loss of asthma control assessed over Weeks 0-16 and over Weeks 0-6.
	
An additional endpoint assessing loss of control between Weeks 0 and 6 was added to help support the time to loss of asthma control analysis.

The posterior probabilities that the ratio of the proportion of subjects with loss of asthma control on GSK3772847 compared with placebo is less than 1.0, 0.75, 0.5 and 0.2 (i.e. more than a 0%, 25%, 50% and 80% reduction) will be produced.
	
The posterior probabilities that the ratio of the proportion of subjects with loss of asthma control on GSK3772847 compared with placebo is less than 1.0, 0.75, 0.7, 0.5 and 0.2 (i.e. more than a 0%, 25%, 30%, 50% and 80% reduction), and greater than 0.6 (i.e. less than a 40% reduction) will be produced.
	
The additional posterior probabilities of the ratio of the proportion of subjects with loss of asthma control on GSK3772847 compared with placebo being <0.70 (more than a 30% reduction) and >0.60 (less than a 40% reduction) were added to assist internal decision making.

Protocol	Reporting & Analysis Plan	
Statistical Analysis Plan	Statistical Analysis Plan	Rationale for Changes

Endpoints included:
 
 
• Proportion of participants with a <math>\geq 0.5</math> point ACQ-5 score increase from baseline.
 
• Proportion of participants who have pre-bronchodilator FEV1 decrease from baseline (measured at the end of Run-in) <math>> 7.5\%</math>.
 
• Proportion of participants where inhaled corticosteroids (ICS) cannot be titrated in accordance with the pre-defined schedule.
 
• Proportion of participants who have a significant asthma exacerbation (requiring OCS and/or hospitalisation).
 
• Proportion of participants with a clinically significant asthma exacerbation or inability to titrate ICS according to the pre-defined schedule
 
• Proportion of participants with <math>\geq 0.5</math> point ACQ-5 score decrease from baseline (responder) at each week from Week 1 to Week 16.
 
• Proportion of St. George's Respiratory Questionnaire (SGRQ) responders (at least a 4 unit improvement from baseline) at Weeks 4, 8, 12 and 16.
 
	
Endpoints to be summarised and not analysed.
	
Due to participants being withdrawn after they reach one component of loss of control, there is no information available for the other components/ ACQ-5 /SGRQ after this date. As a result the numbers of the subjects who have useable data are very small, and any estimates will be biased, so informative decisions can't be made. The data must still be summarised to comply with disclosure rules for pre-specified secondary endpoints.

The minimum detectable effect for the sample size calculations is reported as 31% corresponding to a proportion with loss of control on GSK3772847 of 28%.
	
The minimum detectable effect for the sample size calculations is reported as 36% corresponding to a proportion with loss of control on GSK3772847 of 28%.
	
A typographical error in the protocol which meant that minimum detectable effect was incorrectly reported as 31%, this has been corrected in the RAP.

## 2.2. RAP Amendments

Revision chronology:

RAP Section	Amendment Details
Reporting and Analysis Plan_207597_Final_V01 [20-DEC-2018]	
Reporting and Analysis Plan_207597_Amendment_Final_V01	
Analysis of components of loss of asthma control and responder analysis	
 
Analysis of components of loss of asthma control and responder analysis were removed as explained in Section 2.1.
 

Bayesian Analysis	
 
Additional information provided on the Bayesian logistic regression including starting values, set seeds and thinning options.
 
The posterior probabilities of the ratio of the proportion of subjects with loss of asthma control on GSK3772847 compared with placebo being <0.70 (more than a 30% reduction) and >0.40 (less than a 40% reduction) were added to assist internal decision making.
 

Repeated Measures Analysis	
 
Information on the variance-covariance matrix and use of the OM option added.
 

Treatment Discontinuation Date	
 
Derivation added for treatment discontinuation date
 

Sample Size	
 
A typographical error in the protocol which meant that minimum detectable effect was incorrectly reported as 31%, this has been corrected in the RAP amendment.
 

Tables, Listings and Figures	
 
Minor clarification/typographical errors in output titles and associated RAP text were added.
 

[figure not shown]
### 2.3. Study Objective(s) and Endpoint(s)

Objectives	Endpoints
Primary	

 
To evaluate the efficacy of GSK3772847, compared with placebo, administered intravenously every 4 weeks for 12 weeks (Week 0 – Week 12, 4 doses in total) in participants with moderately severe asthma.
 
	
Primary – Proportion of participants with loss of asthma control over Weeks 0-16 where 'loss of asthma control' is defined as at least one of the following:
 
 
Asthma Control Questionnaire (ACQ-5) score increase from baseline (measured at the end of Run-in) <math>\geq 0.5</math> point or
 
Pre-bronchodilator Forced expiratory volume in 1 second (FEV1) decrease from baseline (measured at the end of Run-in) <math>>7.5\%</math> or
 
Inability to titrate inhaled corticosteroid according to the pre-defined schedule or
 
A clinically significant asthma exacerbation (requiring oral corticosteroid [OCS] and/or hospitalisation).
 

Secondary	

 
To evaluate other aspects of efficacy of GSK3772847 compared with placebo in participants with moderately severe asthma.
 
	
Other efficacy endpoints (at or by Week 16):
 
 
Proportion of participants with a <math>\geq 0.5</math> point ACQ-5 score increase from baseline.
 
Proportion of participants who have pre-bronchodilator FEV1 decrease from baseline (measured at the end of Run-in) <math>>7.5\%</math>.
 
Proportion of participants where inhaled corticosteroids (ICS) cannot be titrated in accordance with the pre-defined schedule.
 
Proportion of participants who have a significant asthma exacerbation (requiring OCS and/or hospitalisation).
 
Proportion of participants with loss of asthma control over Weeks 0-6
 
Time to loss of asthma control.
 
Proportion of participants with a clinically significant asthma exacerbation or inability to titrate ICS according to the pre-defined schedule
 
The incidence, mean rate, and total number per participant of hospitalisations or Emergency Room (ER) visits during the study treatment period.
 
Change from baseline in ACQ-5 absolute score at each week from Week 1 to Week 16.
 
Proportion of participants with <math>\geq 0.5</math> point ACQ-5 score decrease from baseline (responder) at each week from Week 1 to
 

Objectives	Endpoints
	
Week 16.
 
 
• Change from baseline in SGRQ total score at Weeks 4, 8, 12 and 16.
 
• Proportion of St. George's Respiratory Questionnaire (SGRQ) responders (at least a 4 unit improvement from baseline) at Weeks 4, 8, 12 and 16.
 
• Change from baseline in pre-bronchodilator FEV1 at Weeks 2, 4, 6, 8, 10, 12, 14, 16.
 
• Change from baseline in mean morning peak expiratory flow (PEF) and mean evening PEF over each four weeks of the 16 week treatment period.
 
• Change from baseline in mean daytime asthma symptom score over each four weeks of the 16 week treatment period.
 
• Change from baseline in rescue medication use (albuterol/salbutamol): mean number of inhalations per day over each four weeks of the 16 week treatment period.
 
• Changes from baseline in night-time awakenings due to asthma symptoms requiring rescue medication use over each four weeks of the 16 week treatment period.
 
• Change from baseline in fractional exhaled nitric oxide (FeNO) at each week measured.
 

 
• To evaluate the safety and tolerability of GSK3772847, compared with placebo administered intravenously every 4 weeks for 12 weeks (Week 0-12, 4 doses in total) in participants with moderately severe asthma.
 
	
 
• Incidence and frequency of adverse events (AEs) and serious adverse events (SAEs).
 
• Change from baseline in vital signs at weeks 1, 2, 4, 6, 8, 10, 12, 14, 16, 20, 24 and 28.
 
• Change between post-dose and pre-dose in vital signs at weeks 0, 4, 8 and 12.
 
• Change from baseline in 12-lead electrocardiogram (ECG) measurements at weeks 4, 8, 12 and 16.
 
• Change between post-dose and pre-dose in 12-lead ECG measurements at weeks 0, 4, 8 and 12.
 
• Change from baseline in 24 hours Holter measurements at weeks 4 and 12.
 
• Change from baseline in clinical chemistry at weeks 2, 4, 8, 12, 16 and 28.
 
• Change from baseline in haematology and cardiac markers at weeks 1, 2, 4, 6, 8, 10, 12, 14, 16 and 28.
 
• Incidence of and titres of anti- GSK3772847 antibodies at weeks 2, 4, 8, 12, 16, 20, 24 and 28.
 

Objectives	Endpoints


To evaluate the pharmacokinetics (PK) of GSK3772847 in participants with moderately severe asthma.

	

Serum concentrations of GSK3772847 by nominal time.

To evaluate the pharmacodynamics (PD) of GSK3772847 in participants with moderately severe asthma.

	

Free and total soluble ST2 levels in serum by nominal time.

Exploratory	

To compare the effect of GSK3772847 with placebo on biomarkers in serum and sputum.

	

Changes from baseline in induced sputum biomarkers (subset) at weeks 8 and 16.

Changes from baseline in exploratory serum markers at weeks 8 and 16.

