## 2.4. Study Design

Overview of Study Design and Key Features	
 
The diagram illustrates the study design timeline from Week 0 to Week 28. It is divided into a Treatment Phase (Weeks 0-12) and a Follow Up Phase (Weeks 16-28). In the Treatment Phase, participants receive a double-blind study treatment every 4 weeks, either GSK3772847 or Placebo, at Weeks 0, 4, 8, and 12. Simultaneously, background therapy is reduced from LABA, Sal, and ICS at Week 0 to FP 500 BID at Week 2, and then further reduced to FP 250 BID, FP 100 BID, and FP 50 BID by Week 10. In the Follow Up Phase, participants receive LABA and ICS from Week 16 to Week 28. Visits are labeled V0 through V14, with an ETP Visit at Week 11.
	
Design Features	
 
The study is a Phase IIa, multicenter, randomised, placebo-controlled, double-blind, stratified, parallel group study.
 

Dosing	
 
Participants will have a two-week Run-in period in which they take a background therapy of fluticasone propionate (FP)/salmeterol 500/50 mcg BID.
 
Following run-in they will be randomised to receive four doses of either GSK3772847 or Placebo intravenously (Week 0, 4, 8 and 12) whilst initially still receiving background FP/Salmeterol 500/50 mcg BID.
 
At Week 2 background therapy will be changed to FP 500 mcg BID only. This will then be reduced by approximately 50 % every two weeks until complete FP discontinuation at Week 10.
 

Treatment Assignment	
 
Participants will be randomised in a 1:1 ratio to receive four doses of either GSK3772847 or Placebo administered intravenously every 4 weeks.
 
Randomisation will be stratified based on participants' baseline peripheral blood eosinophil count which is measured at screening (<150 cells/<math>\mu</math>L, <math>\geq</math>150 cells/<math>\mu</math>L), Randomisation will also be stratified according to whether participants consent to the sputum sub study.
 

Overview of Study Design and Key Features	

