#### 10.1.5. Statistical Analyses / Methods

Endpoint / Variables

 
Percentage change from baseline in free sST2 (On-treatment)
 
Percentage change from baseline in free sST2 (Post-treatment)
 
Percentage change from baseline in total sST2 (On-treatment)
 
Percentage change from baseline in total sST2 (Post-treatment)
 

Strategy for Intercurrent (Post-Randomisation) Events
No intercurrent events are considered for this endpoint. All data will be used as collected.
Model Specification

 
The ratio of post-baseline sST2 values to baseline sST2 values will be log transformed prior to analysis. Note: <math>\text{Log}(\text{post baseline sST2} / \text{baseline sST2})</math> is equivalent to <math>\text{log}(\text{post baseline sST2}) - \text{log}(\text{baseline sST2})</math>.
 
A repeated measures model with terms for treatment, visit, visit by treatment, the logarithm of baseline sST2, the logarithm of baseline sST2 by visit and screening eosinophil strata will be fitted.
 
 
Model Structure:
 
 
The variance-covariance matrix will be assumed unstructured.
 
Kenward Roger (KR) method will be used for calculating degrees of freedom. If the analysis does not run using the KR method then the residual method will be used instead.
 

 
An observed margins (OM) dataset will be used to derive the LS means using coefficients which are based on the subjects used in the analysis. This is a dataset with a row for every subject-visit combination that contains all of the covariates. The OM will be at the average baseline of free sST2 (either On-treatment or Post-treatment according to the model).
 

Model Checking & Diagnostics

 
Distributional assumptions underlying the model used for analysis will be examined by obtaining a normal probability plot of the residuals and a plot of the residuals versus the fitted values (i.e. checking the normality assumption and constant variance assumption of the model respectively) to gain confidence that the model assumptions are reasonable.
 

Model Results Presentation

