12.2. Appendix 2: Schedule of Activities

12.2.1. Protocol Defined Schedule of Events

Procedure	Pre-Screening 	Screen Run-in	Treatment Period										Follow-up Period  (± 3 days)			Notes
			± 2 days			± 3 days							12	13	14	
Visit	0	1	2 	3	4	5	6	7	8	9	10	11 (ETP or EW)	12	13	14	1. Pre-screening and screening can occur on the same day 2. FU period to start 4 weeks after ETP or EW visit. 3. Visit 2 = Day 1 (first dose of IP).
Week	-4~-2	-2	0	1	2	4	6	8	10	12	14	16	20	24	28	
Study Day	-28~-14	-14	1	8	15	29	43	57	71	85	99	113				
Informed consent (ICF)	X															
Genetic ICF		X														
ICF for sputum		X														
Inclusion and exclusion criteria		X														
Randomisation Criteria			X													
Demography	X															
Full physical exam including height and weight		X														
Medical history (includes substance abuse)		X														Substances [Drugs, Alcohol, tobacco] and family history of premature CV disease]: [including cardiovascular medical history]
Laboratory																

Procedure	Pre-Screening 	Screen Run-in	Treatment Period										Follow-up Period  (± 3 days)			Notes
			± 2 days			± 3 days										
Visit	0	1	2 	3	4	5	6	7	8	9	10	11 (ETP or EW)	12	13	14	1. Pre-screening and screening can occur on the same day 2. FU period to start 4 weeks after ETP or EW visit. 3. Visit 2 = Day 1 (first dose of IP).
Week	-4~-2	-2	0	1	2	4	6	8	10	12	14	16	20	24	28	
Study Day	-28~-14	-14	1	8	15	29	43	57	71	85	99	113				
Laboratory assessments		X 	X 	X	X 	X 	X	X 	X	X 	X	X 			X 	Haematology (including eosinophil count) and cardiac markers measured at all clinic visits. 1. Clinical chemistry (including liver chemistry). 2. Routine urinalysis at screening (Visit 1)
Pregnancy test 		X 	X 			X 		X 		X 		X	X	X	X	1. Test for women with child bearing potential. 2. Serum pregnancy test at V0/V1. 3. Test to be performed pre-dose during the treatment period.
[HIV, Hep B and Hep C screen]		X														A confirmatory negative Hepatitis C RNA test must be obtained, to be able to enrol participants with positive Hepatitis C antibody due to prior resolved disease. If test has been performed within 3 months prior to first dose of study treatment, testing at screening is not required.

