**12.3. Appendix 3: Assessment Windows**

**12.3.1. Definitions of Assessment Windows for Analyses**

Nominal visits will be used and no windowing will be applied for analysis.

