## 12.4. Appendix 4: Study Phases and Treatment Emergent Adverse Events

### 12.4.1. Study Phases

Assessments and events will be classified according to the time of occurrence relative to study treatment start date.

Study Phase for all data except efficacy	Definition
Pre-treatment	Date $\leq$ Study Treatment Start Date
On-treatment	Study Treatment Start Date < Date $\leq$ Study Treatment Stop Date + 28 days
Post-treatment	Date > Study Treatment Stop Date + 28 days

Study Phase for efficacy	Definition
Pre-treatment	Date $\leq$ Study Treatment Start Date
On-treatment	Study Treatment Start Date < Date $\leq$ Date of discontinuation from study treatment Or if the participant did not discontinue early from study treatment Study Treatment Start Date < Date $\leq$ Study Treatment Stop Date + 28 days
Post-treatment	Date > Study Treatment Stop Date + 28 days

Once participants withdraw from study treatment they immediately restart their standard of care medication (ICS/LABA). As a result, any data collected past this point will have been impacted by the standard of care medications and any estimates produced biased by the additional use of ICS/LABA. For this reason, data post withdrawal from study treatment is not included in the on-treatment efficacy analysis.

The post treatment definition is the same for efficacy and safety analysis.

Completion of study epoch's will be defined as the following:

Study Phase	Definition of Completion
Run-in	Randomised into study and received first dose of study treatment
Treatment	Completed Week 16 visit or withdrew from treatment phase due to loss of asthma control
Follow up	Completed 12 week follow-up period

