## 12.7. Appendix 7: Reporting Standards for Missing Data

### 12.7.1. Premature Withdrawals

Element	Reporting Detail
General	
 
• Subject study completion (i.e. as specified in the protocol) was defined as either completing the 16 week treatment period and three month safety follow up, or withdrawing from the treatment period early due to loss of asthma control and completing the three month safety follow up period.
 
• Withdrawn participants were not replaced in the study, unless the participants were withdrawn due to sites failing to comply with GCP.
 
• All available data from participants who were withdrawn from the study will be listed and all available planned data will be included in summary tables and figures, unless otherwise specified.
 
• Withdrawal visits will be slotted as per Appendix 3: Assessment Windows or will be summarised as withdrawal visits.
 

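### Follow-up visits restart their clock at early withdrawal but have only the labels Week 20, 24 and 28, so nominal-time PK and post-treatment sST2 displays mix times since last infusion and numbers of infusions

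*SAP*

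**What the plan says.** SAP section 2.4 has participants "randomised to receive four doses of either GSK3772847 or Placebo intravenously (Week 0, 4, 8 and 12"). The schedule in section 12.2.1 gives Visit 11 one shared column for end of treatment (ETP) and early withdrawal (EW). It gives Visits 12, 13 and 14 one column each, headed Week 20, 24 and 28. The note to both the main schedule and the PK/sST2 sampling table reads "FU period to start 4 weeks after ETP or EW visit". PK and sST2 are sampled at all three visits.

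Early withdrawers belong in this follow-up. Section 12.7.1 counts as study completion "withdrawing from the treatment period early due to loss of asthma control and completing the three month safety follow up period", and section 12.4.1 defines completion of the follow-up epoch as "Completed 12 week follow-up period".

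For analysis, section 12.3.1 states "Nominal visits will be used and no windowing will be applied for analysis", and section 12.5.2 uses planned rather than actual time in summaries, figures and models. The endpoint in section 2.3 is "Serum concentrations of GSK3772847 by nominal time", with a matching endpoint for sST2. Table 1 gives the reason: "Endpoint updated to use nominal time so that all data collected is summarised".

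Section 10.1.5 models "Percentage change from baseline in free sST2 (Post-treatment") and the same quantity for total sST2. The terms are treatment, visit, their interaction, log baseline, its interaction with visit, and eosinophil stratum. No intercurrent event removes data, and no term reflects infusions received or time since the last one.

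**The concern.** A follow-up PK curve is read as drug washout, and a post-treatment sST2 curve as recovery of the target. Both readings need the horizontal axis to mean time since dosing. For completers the nominal week does that. For a participant who left treatment early it does not: at the visit labelled Week 20, that person may have had one infusion and be in actual Week 5.

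Early withdrawal is part of the design, because loss of control is the primary endpoint and takes participants off treatment. The mixture under each label therefore depends on how many active participants lost control, and when. The same drug kinetics could give different follow-up curves in two trials with different loss-of-control rates.

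**Working it through.** **Inputs from the SAP.** Infusions at Weeks 0, 4, 8 and 12 (section 2.4); clinic reviews at Weeks 1, 2, 4, 6, 8, 10, 12, 14 and 16; Visits 12, 13 and 14 at ETP/EW week + 4, + 8 and + 12 (section 12.2.1); post-treatment means more than 28 days after treatment stop (section 12.4.1).

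**Assumption.** No infusion is given at an EW visit that falls on a dosing week. If one were, the lowest value would move towards 4 weeks.

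**Step 1, the plan's own labels.** A completer has ETP at Week 16: 16 + 4, 16 + 8, 16 + 12 = Weeks 20, 24, 28. The last infusion was at Week 12, so time since it is 8, 12 and 16 weeks. The labels reproduce for completers.

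**Step 2, early withdrawal.** Weeks since last infusion = EW week + 4 (or 8, 12) − week of last infusion.

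| EW week | Infusions | Actual week of Visit 12 | Weeks since last infusion at Visits 12 / 13 / 14 |
|---|---|---|---|
| 1 | 1 | 5 | 5 / 9 / 13 |
| 2 | 1 | 6 | 6 / 10 / 14 |
| 4 | 1 | 8 | 8 / 12 / 16 |
| 6 | 2 | 10 | 6 / 10 / 14 |
| 8 | 2 | 12 | 8 / 12 / 16 |
| 10 | 3 | 14 | 6 / 10 / 14 |
| 12 | 3 | 16 | 8 / 12 / 16 |
| 14 | 4 | 18 | 6 / 10 / 14 |
| 16 (completer) | 4 | 20 | 8 / 12 / 16 |

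Allowing EW in any whole week adds 7 weeks at Visit 12. Completers included, the Week 20 label covers 5–8 weeks since last infusion (actual Weeks 5–20), the Week 24 label 9–12 (Weeks 9–24) and the Week 28 label 13–16 (Weeks 13–28). Each label holds one to four infusions. The ±3-day window widens the first range to (35 − 3)/7 = 4.6 up to (56 + 3)/7 = 8.4 weeks. All of these exceed 28 days, so every such Visit 12 enters the post-treatment sST2 model.

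**Step 3, illustrative size for PK.** The SAP gives no half-life. Assume one-compartment decline with half-life h of 1.5 to 4 weeks and superpose doses: C(t) = Σ 2^(−(t − dose week)/h). Take the ratio of an early withdrawer at Visit 12 to a completer at Week 20.

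- h = 1.5, EW Week 1: 2^(−5/1.5) = 0.0992; completer 0.0294; ratio 3.37 (the highest).
- h = 4, EW Week 4: 2^(−8/4) = 0.25; completer 0.25 + 0.125 + 0.0625 + 0.03125 = 0.469; ratio 0.53 (the lowest).

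Suppose 28% of active participants are affected, spread evenly over the eight reviews before Week 16. The geometric mean is then multiplied by exp(0.28 × mean log ratio):

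| Half-life (weeks) | Mean log ratio | Multiplier |
|---|---|---|
| 1.5 | 0.564 | 1.17 |
| 2 | 0.352 | 1.10 |
| 3 | 0.091 | 1.03 |
| 4 | −0.071 | 0.98 |

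The shift in the mean can be small because fewer infusions lower the concentration while earlier sampling raises it. The spread between participants does not cancel.

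No comparable figure can be given for sST2, as the SAP has nothing on its recovery.

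**The case against.** **Labels.** The SAP never says in words that an early withdrawer's Visits 12–14 keep the Week 20, 24 and 28 labels. Section 12.7.1 also allows withdrawal visits to be summarised as such. It is true that retention is inferred. But those are the only labels provided, windowing is ruled out, and the section 12.7.1 rule does not mention the follow-up visits.

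**Deviations and listings.** Section 12.5.2 promises to assess major departures from planned times as appropriate, and listings show actual times. Neither helps: a restarted clock is the planned schedule, not a departure from it, and listings do not change the tables and plots.

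**Size and importance.** The size rests on an outside half-life and an assumed even spread of withdrawals. At 3 to 4 weeks the mean moves by only +3% to −2%, and the 3.4-fold ratio is a single extreme case. Withdrawal at Weeks 4, 8 or 12 gives exactly a completer's time since last infusion, though with fewer infusions. PK is purely descriptive (section 9.1.4). All of this stands and limits the weight of the point.

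**Stronger readings to resist.** A reader might infer that 28–44% of participants leave early. Section 2.6 does not say so: 44% is the assumed placebo rate of loss of control, and 28% is the active proportion at the smallest difference that would reach significance. Both also count losses first found at Week 16, where no clock shift arises. A reader might also infer that the sST2 model should be re-indexed by weeks since infusion or adjusted for number of infusions. Individuals contribute separate triplets (5/9/13, 6/10/14, 8/12/16), so many pairs of times never occur in one person and the specified unstructured covariance could not be estimated. Number of infusions is a post-randomisation consequence of loss of control, so conditioning on it could bias the treatment ratio.

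**Conclusion.** The point holds. Followed as written, the SAP pools one to four infusions under each follow-up label, with a spread of three weeks in time since the last infusion. Table 4.1 and Figure 6.1 (PK) at follow-up, and Tables 6.3, 6.4, 6.7 and 6.8 with Figures 6.6 and 6.8 (post-treatment sST2), therefore do not describe washout or recovery at a defined time since dosing.

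The timing result follows from the schedule alone, given that the printed labels are retained and no infusion is given at the EW visit. The share affected is unknown from the SAP. The −2% to +17% shift in the PK geometric mean at the Week 20 label is illustrative. The documents do not support a claim that the sST2 ratios are biased by a known amount or direction. The primary endpoint and the efficacy and safety conclusions are untouched.

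**What to change.** 1. For early withdrawers, label Visits 12–14 as + 4, + 8 and + 12 weeks after ETP/EW instead of study Weeks 20, 24 and 28, and say so in section 12.3.1.
2. Present PK and sST2 summaries and plots after the last infusion by weeks since last infusion, split by number of infusions received.
3. Add a separate display for participants who received four infusions and completed Week 16, described as a selected subset because they did not withdraw early.
4. Keep visit as the repeated factor in the post-treatment sST2 models. Describe the resulting ratios as relative to end of treatment or withdrawal, not to a study week. Do not add number of infusions as a covariate, and do not replace visit under the unstructured covariance.

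The cost is SAP wording, one time variable derived from dates already collected, and some extra displays with small cells. Summarising by weeks since last infusion still meets the stated aim of using all data collected.
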